3.2 SECONDARY OUTCOME(S)

Secondary study endpoints, events, or outcomes you will be evaluating or observing.

Secondary outcomes include:

- Fall rates
- Quality of life

3.3: EXPLORATORY OUTCOME(S)

Other exploratory variables include:

- Functional strength and balance
- Social resources
- Readiness
- Self-regulation
- Pain (intensity and impact on function)
- Medication inventory
- Sex as a biological variable
- Covid 19 (impact of mitigation/ containment efforts on health and physical activity)

CHAPTER 4 - STUDY INTERVENTION

4.1: DESCRIPTION

Intervention description.

Dose and delivery. We carefully considered the dose of 8 weekly contacts, each lasting 90 minutes, based on triangulated data from our prior research and feedback from community stakeholders. Our prior research⁹ and the CDC compendium of fall prevention interventions⁶¹ describe a broad range of doses that elicit promising effects with 8 weeks-12 contact hours on the low side of the range and 52 weeks-104 contact hours on the high side of the range. Also, our preliminary studies showed intervention session attendance was good across conditions and in post-intervention interviews, participants indicated this dose was acceptable: some even suggested we increase intervention duration to 12 weeks. Community stakeholders including older adults, center leaders, and healthcare providers advised us to increase the amount of time spent during contacts from 60 minutes to 90 minutes to ensure participants did not feel “rushed.” They also advised us to conduct intervention and data collection meetings between 9 am and 4 pm, and to limit group size to 4-6.

Adjustments for Coronavirus: March 17, 2020

Intervention visits in this study are done in small group (4 to 6 people) gatherings during which we practice the Otago Exercise Program movements together, and a coach facilitates discussions focused on behavior change strategies being tested. We enroll one cohort of 16 to 24 participants at a time, so they can complete the 8-week course. In

light of the current situation, we will delay future cohorts until we are able to deliver the small group intervention in person again.

However, our current cohort (11 of 13) is in week 6 of the 8-week intervention. Thus, we plan to conduct these by phone conferencing using UMN Zoom. We will not use the video portion of Zoom because not all participants have access to the internet. We will conduct each meeting according to our intervention manual, which delineates topics for discussion and exercise per Otago protocol. Similar to in-person intervention meetings and when participants perform these exercises at home independently (2 times per week to every day), there is a small risk of discomfort or injury. Consistent with our protocol and the Otago Exercise Program manual we will minimize the risk using several strategies. First, the exercises in Otago are considered safe for older adults, including those with frailty and multiple chronic conditions. Second, we will ensure that all phone conference participants have water, and are near sturdy structures during the exercises, such as a non-rolling chair or a counter. Third, we will remind participants to stop exercising if they feel discomforts such as joint pain or shortness of breath. Finally, at this point in the intervention, all participants who will participate in the conference call have mastered the exercises and know how to personally adapt them according to ability, comfort, and preferences.

Table 3 highlights condition and content by time. Each contact is 90 minutes: 10 for questions and answers; 40 for Otago PA; 20 for interpersonal behavior change strategies; 20 for intrapersonal behavioral change strategies; and, in lieu of behavioral change strategies--20-40 for attention control topics related to Health & Age, based on the National Institute of Aging website, Health & Aging.⁶²

Table 3. Condition, Content, and Time

Time in Minutes	Condition and Content			
	Otago/PA	Otago/ PA + Inter-personal	Otago/ PA + Intra-personal	Otago/ PA + Inter-personal + Intra-personal
10	Q& A	Q&A	Q&A	Q&A
40	Otago	Otago	Otago	Otago
20	Health & Age	Inter-personal	Health & Age	Inter-personal
20	Health & Age	Health &Age	Intra-personal	Intra-personal

The social milieu in each small group meeting will support friendly and positive interactions and discussions guided by curricula topics and objectives. All content (experimental, attention control, core) is summarized in the next six paragraphs.

Experimental component: Interpersonal content. In the interpersonal component, a dialogue between small group participants will be facilitated focusing on their knowledge and experiences integrating fall-reducing PA into their social routines, providing and receiving social support for exercise, and using relevant community resources. Non-competitive, friendly, social comparison and exchange will also be facilitated, focusing on sharing different ways to practice fall-reducing PA; PA patterns derived from personal PA-monitor data; what others think about PA; and sharing PA data with important others (e.g., family, friends, providers).

Experimental component: Intrapersonal content. The intrapersonal component discussions will focus on guiding participants to develop, and modify as needed, personally meaningful goals and plans, using the National Institute on Aging's Go4Life⁶³ goal- setting and weekly planning PA worksheets. Discussions will also address personal barriers management; habit formation; coping with potential setbacks; and self-monitoring PA outcomes, congruent with personal goals.

Attention control content: Health & Age. Similar to our preliminary research, we will provide attention control topics about Health & Age, from the National Institute of Aging website including information about falls, pain, nutritional supplements, sleep, hearing, memory, and vaccinations.

Core content: Otago (PA protocol). The evidence-based Otago protocol guides the core fall-reducing PA content in this study. It is feasible and effective in community-dwelling older adults, including those with multiple chronic conditions (e.g., osteoporosis), pain, and frailty.^{10, 13, 64} Our team and others have successfully implemented the Otago PA protocol in small groups.^{13, 49} The overarching goal of Otago in this study is to facilitate participants' mastery and individualization of specific movements and exercises so they can self-direct their practice of these outside the small group setting. The program includes 5 flexibility movements (back extension and ankle, head, neck, trunk movements), 5 leg strengthening exercises (knee extensor, knee flexor, hip abductor, ankle plantar flexes, ankle dorsiflexes), 12 balance movements (knee bends, backwards walking, walking and turning, sideways walking, tandem stance, tandem walk, one leg stand, heel walking, toe walking, heel-toe walking backwards, sit to stand, stair walking), and a walking plan. The number, intensity and duration of movements are gradually increased.⁶⁵ Thus, time spent on the combined movements and exercises slowly increase across the 8-week intervention from approximately 15 to 35 minutes per meeting. We encourage participants to increase their walking time by 20% of their baseline average -up to 30 minutes per day. We also encourage participants to self-direct their practice of Otago PA that they have mastered, outside the small group meetings. Some choose to practice their leg-strengthening and balance PA during one timeframe. Others choose to practice different types of PA at different times of the day (e.g., balance exercises while waiting for coffee to brew, leg-strengthening exercises while watching TV). Similarly, some choose to take 30-minute walks once per day, others prefer to take break their walking time up into 10 minute bouts. In total, participants are encouraged to practice their personalized Otago PA protocol every other day (approximately 70 minutes per week) and to walk approximately 30 minutes per day (150 minutes per week), which is consistent national and international PA guideline recommendations for minimal PA among older adults, including those with multiple chronic conditions.⁵⁹ When participants cannot practice the amounts of PA recommended in Otago due to health conditions, they are encouraged to be as physically active as their abilities and conditions allow.^{59,66}

Core content: PA-monitor. We will use Fitbit, a commercially available PA-monitor. [name]. (Consultant) is an expert in mobile health who will advise our research team about the model of Fitbit and provide input about managing and analyzing accelerometer data, which we accomplished in the past using Fitabase.⁶⁷ Features of PA-monitors that were important to participants in our preliminary studies include displays with real-time feedback in the form of actual steps and distance, as well as positive messages that encourage about PA.^{36,50} Features essential for researchers include built-in accelerometers that accurately measure steps and PA duration. Each device will be set up and programmed prior to distributing. We will assign a unique monitor identification number to each monitor; not related to participant's study ID or personally identifying information. Also, we will program monitor parameters (e.g., step goals) to minimal levels. During the baseline data collection meeting, we will provide each participant with a PA-monitor and a 15-20-minute orientation to review and demonstrate its basic functions: wearing, charging, and reading the display. Participants will also have the opportunity to return demonstrate. In addition, RAs will be available to help participants troubleshoot, as needed, via telephone and in person, after intervention meetings.

Intervention meetings include discussions about the PA-monitors, but topics vary per assigned condition (see **Table 4**) above.

[figure not shown]
CHAPTER 5 – PROCEDURES INVOLVED

5.1 STUDY DESIGN

Experimental. We will address this proposal's aims and hypotheses using a 2x2 factorial experiment where one factor represents receipt of an interpersonal intervention component (No vs Yes) and the second factor represents receipt of an intrapersonal intervention component (No vs Yes). Three hundred and eight community-dwelling older adults will be randomized to 1 of 4 conditions, which represent distinct combinations of experimental components (sets of interpersonal and intrapersonal behavior change strategies) and core intervention content (evidence based physical activity protocol and a physical activity monitor). The study will be implemented in 13 waves over 48 months, within Minneapolis and St. Paul community centers. Interventions for each condition will be delivered to small groups of participants (4-6) randomized to the same condition. These small groups will meet every week for approximately 90 minutes over the course of 8 weeks.

5.2 STUDY PROCEDURES

Figure 3 outlines an overview of participant activities in this study. Participants at least 70 years old with self-reported physical activity (PA) levels below national recommendations will be recruited from the Minneapolis-St. Paul, Minnesota metro region. Participants who respond to newspaper advertisements or fliers will call a central project telephone number to be scheduled for initial eligibility screening by the study coordinator.

Screening. Potential participants who respond to newspaper advertisements or fliers will call a central project telephone number to be scheduled for initial eligibility screening by a trained study coordinator using the screening case report form in the Research Electronic Data Capture (REDCap). Screening questions will include:

- Age and date of birth
- History of lower extremity surgery
- Fall risk factors

- Three surveys:
 1. The Exercise and Screening for You (EASY)⁵⁶
 2. The Rapid Assessment of Physical Activity (RAPA) ⁵⁴
 3. A six-item screener for cognitive function (name three items; recall three items; year; month; day of the week)

Consenting and Baseline Data Collection. If potential participants are eligible and interested, trained study staff will meet them in person to obtain written informed consent.

Once consenting is complete, the trained study staff will conduct baseline measures: (a) an interview including self-report measures (50 minutes); (b) observation of functional gait and balance (10 minutes); (c) initial or orientation to PA monitor--Fitbit (20 minutes); (d) after a one week practice period, participants and RA will meet again to confirm that the PA- monitor is acceptable and usable, and to begin the baseline 7 day PA data capture period (15 minutes); (e) after wearing the PA-monitor for 7-10 days, at least 10 hours each day, participants and study staff will meet again to complete the PA-data capture (15 minutes). Combined, the baseline procedures will require approximately 2 hours, and be completed over the course of 2 weeks.

Randomization: Once potential participants have provided consent and baseline data collection is complete, they will be formally randomized to 1 of 4 study conditions. They will begin the 8-week intervention within 8 weeks of enrollment/ randomization.

There will be rare situations when a participant is enrolled and randomized in the study, but is unable to begin or complete the 8-week intervention due to unforeseen changes in their life such as the death of a family member or the sudden need for medical treatments. In such situations, participants will be given the option to: (a) delay their participation in the 8-week intervention portion of the study, (b) withdraw from the 8-week intervention, but undergo one or more of the post-intervention data collection meetings, or (c) withdraw from all aspects of the study. Trained study staff will identify and track such situations in REDCap.

If participants choose option (a), they will **not** be re-randomized. Rather, researchers will invite them to an 8-week intervention course/ condition to which they were originally randomized, but that is scheduled to occur in a later time-frame.

Research staff will repeat screening to determine continued eligibility.

- If participants remain eligible, research staff will repeat baseline assessments within 8 weeks of the participant's delayed start of the 8-week intervention.
- If participants become ineligible---, reason(s) for ineligibility will be documented.

The analyst will compare and report the results of repeated baseline measures for subjects who choose option (a) and remain eligible for the study. If the differences between the repeated baseline measures are not significant, the first set of values will be used in inferential analyses. If the differences between the repeated baseline measures are significant, the second set of values (those most proximal to the intervention delivery) will be used in inferential analysis. A description of this will be included in all reports.

Research Outcome Data Collection. Trained research assistants will collect all data. They will be trained to accurately collect and manage data and to interview older adults in ways that are non-threatening, friendly, and respectful. Data will be derived from in-person interviews, observations, monthly fall calendars, and objectively measured PA parameters from accelerometers within participant's commercially available PA-monitors.

In-person interviews include scripted, structured interviews asking questions from these validated tools (all widely used) at the following time points:

- Baseline only: Demographic*
 - Biological
- Baseline; immediately post-intervention; 6 months' post-intervention; and 12 months post-intervention:
 - Pain via the Brief Pain Inventory-short form (Tan, 2004; Mendoza, 2006)^{89,90}
 - Medication Inventory (see Appendix 2)
 - Self-reported health and Fall Risk (Stevens, 2013; Kunkel, 2011)^{55,75}
 - Impact of the COVID-19 Pandemic and Accompanying Mitigation Efforts on Older Adults' physical activity and wellbeing¹¹⁰
 - Social Support and Exercise Survey (Family and Friends) (Sallis et.al , 1987)⁸⁰
 - Duke--UNC Functional Social Support Questionnaire*
 - Index of Readiness (Fleury, 1994)²²
 - Self-Efficacy for Exercise (Resnick & Jenkins, 2000)⁸¹
 - Index of Self-Regulation (Fleury, 1998)⁸⁴
 - Physical Activity Enjoyment Scale-8
 - Behavioral Regulation in Exercise Questionnaire (Markland & Tobin, 2004)⁸³
 - Life-Space Mobility¹¹¹
 - Physical Function-Short Form-6b (PROMIS; Rose, 2008)⁷⁹
 - Physical Activity Scale For The Elderly PASE⁷²
 - Health and Physical Activity Resources Survey (CIRS)¹¹²
 - Group Cohesion**
 - Quality of Life: Global Health Scale Patient-Reported Outcomes Measurement Information System, including items that address physical and social function (PROMIS) (Hays, 2009)⁷⁶

*Administered at baseline only

**Administered immediately post-intervention only

Coronavirus adjustments: March 17, 2020

Assessment visits, which are structured interviews lasting approximately 45 to 90 minutes, will occur over the phone for the duration of new Coronavirus recommendations. We will notify the participants of this change. Our researchers will adjust their schedules according to our participants' availability and mail them information as needed.

The SPPB portion of the assessments, which require in person observation, will be delayed until Coronavirus restrictions are lifted.

Observations of functional strength and balance include the Short Physical Performance Battery at baseline; immediately post-intervention; 6 months' post-intervention; and 12 months post-intervention.⁷⁷ This battery includes timed repeated chair stand, semi-tandem, side by side, tandem balance testing, and a timed walk. Scores for each item are summed for a total score

ranging from 0-12 (12 indicates no impairments). The gradient of resulting scores validly reflects variation in lower extremity strength in older adult populations, and is predictive of progressive disability. It also demonstrates that the timed walk is predictive of catastrophic disability. The test will be discontinued if either the participant or the RA perceives it is unsafe to proceed.

Fall calendars will be sent to participants monthly with instructions to document injurious and non-injurious falls by day of the month, as well as related circumstances and consequences on the questionnaires, which are located on the back of each calendar.^{73,74} They are mailed to participants one week prior to the beginning of each month. Participants will document prospectively on the calendars throughout the month, and then return them to the research team in the stamped, addressed return-envelope provided. We will call participants who do not return calendars to identify and problem-solve barriers to using them. We will also call participants who report falls to further explore fall circumstances and consequences.

Objectively measured PA will be captured via the commercially available PA-monitors at baseline; immediately post-intervention; 6 months post-intervention; and 12 months post-intervention. In this study we will use Fitbit Ones™ unless they are not available; in which case we will choose another equivalent Fitbit model. Participants will be asked to wear their Fitbits during data collection periods for up to 10 hours daily, for 7-10 consecutive days. Each of their PA-monitors will be assigned an alphanumeric ID and will be registered under that ID, which is not connected to their study documents or personally identifiable information. Data, PA intensity classifications and number of steps walked (day total, hour, and minute-by-minute intervals) will be captured by Fitabase, a fully hosted, cloud-based software that implements robust industry standards to maintain secure research databases and keeps data private.⁶⁷ Fitabase enables the aggregation, reduction, visualization and management of data prior to downloading it into Research Electronic Data Capture (REDCap). Both databases meet privacy and security required when conducting research responsibly.

Process evaluation. Because this is a behavioral randomized control trial we will evaluate, formatively and summatively, processes involved with implementing the intervention as planned. In particular, we will (a) examine the extent to which the intervention was delivered as planned by each interventionist using indices of procedural consistency by the interventionist and by the principal investigator (PI) reviewing randomly selected audiotapes of intervention meetings, as well as field notes from each meeting; (b) the extent to which individual participants received and enacted the intervention using attendance records, tracking progress of each participant's exercises (tracking tools for this are part of the evidence based PA protocol); and, (c) multilevel factors (e.g., individual, social, environmental and institutional) that may influence intervention implementation and effects using semi-structured interviews of randomly selected study participants (n=30), from the perspectives of leaders within community centers that host this intervention (n= 5). These interviews will be audiotaped and analyzed using content analyses.

Attendance after each meeting documented by the interventionist. If a participant misses more than one meeting, trained study staff will call them to discuss and problem solve any barriers to attendance.

The interventionists will document attendance and field notes after each meeting. They will also track individual participant progress with the exercises that are included in the evidence-based protocol, which is part of the standard administration procedures of the protocol.

After completing the 8-week intervention, participants will be scheduled for data collection meetings immediately post-intervention (e.g., during the week after the intervention ends); 6

months post-intervention; and 12 months post-intervention. Procedures used during these data collection meetings will be similar to the aforementioned baseline procedures, minus the 1 week practice period. Combined, post-intervention procedures will require 4.5 hours (90 minutes per data collection time point).

Semi-structure interviews to ascertain participants' perspectives of multi-level Barriers and Facilitators of implementation and effect immediately post study.

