9.1 INCLUSION CRITERIA

All potential participants will be screened by trained study staff for inclusion based on the following criteria:

Inclusion Criteria:

- ≥70 years of age
- English speaking
- Low PA as determined by the Rapid Assessment of Physical Activity Survey⁵⁴
 - Aerobic sub score 1-4 – Does not participate in endurance exercise such as walking more than 150 minutes per week, and / or
 - Strengthening/Balance activities sub score of 0 – Does not participate in strengthening and/or balance exercises more than once per week
- One or more fall risk factors as determined by CDC, Steadi fall risk screener⁵⁵
 - One or more falls in the last year
 - Unsteadiness when standing or walking
 - Worries about falling
- Participants who self-report the following symptoms will require clearance from a primary provider (as guided by the Exercise and Screening for You Questionnaire):⁵⁶
 - Pain, tightness or pressure in chest during PA (walking, climbing stairs, household chores, similar activities) *that have not been checked and/ or treated by a healthcare provider*
 - Current dizziness *that have not been checked and/ or treated by a healthcare provider*
 - Current, frequent falls *that have not been checked and/ or treated by a healthcare provider*

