We believe participation in this research will yield benefits for participants. Mastery of physical activities within the Otago PA protocol will provide participants with skills and knowledge to practice these exercises safely at home or in other environments of their choice. The behavioral change strategies in the intervention have the potential to motivate participants continued engagement in PA. Participants will also receive a PA-monitor for self-tracking and support to use it as well as interpret its data.

CHAPTER 17 – DATA MANAGEMENT

17.1: DATA ANALYSIS PLAN

Statistical analysis. Descriptive statistics (means, standard deviations, ranges for continuous variables and counts/ percentages for categorical variables) will be used to summarize biologic, demographic, outcome, and exploratory measures by treatment arm, actual and projected accrual, attendance and retention rates, quality control data (e.g., missing data), and fidelity data. Tables, graphs and charts will be used to visualize data when appropriate. Enrollment summaries will be reviewed at weekly research staff meetings throughout enrollment phases and every month during non-enrollment phases. Differences by randomly assigned condition will be assessed with one-way ANOVA tests for continuous and Fisher's exact test or chi-square tests for categorical variables as appropriate. Any identified confounders will be adjusted for in subsequent analyses. All analyses will be pre-planned and conducted while masked to condition.

We will include all cases in analyses, regardless of intervention attendance rates or attrition. Missing data will be analyzed. We anticipate, based on preliminary research that the rate of missing data will be low and similar across conditions, but that it may be associated with severe illness that leads to dropout or inability to capture follow- up PA data. Thus, similar to preliminary analyses, we will conduct a sensitivity analysis of complete cases and imputing worst case carried forward.

Primary Aim: Intervention component effects on PA will be assessed using 2x2 full factorial ANCOVA models with duration of total PA as the outcome (average minutes per

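### Delayed participants are re-screened on entry criteria after randomization, and the plan does not keep those who fail in follow-up and analysis

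*Combined protocol and SAP*

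**What the plan says.** Section 5.2, after the randomization paragraph, deals with people who already have an allocation. It begins "There will be rare situations when a participant is enrolled and randomized in the study" and covers anyone who "is unable to begin or complete the 8-week intervention due to unforeseen changes in their life". Such a person may (a) delay, (b) leave the course but attend one or more later assessments, or (c) leave the study. Those who delay are not re-randomized; they wait for a later course in their assigned condition.

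For them, "Research staff will repeat screening to determine continued eligibility". Screening, as listed in sections 5.2 and 9.3, covers age, leg surgery, fall risk factors, the EASY and RAPA surveys and a cognitive screener. Section 9.1 requires "Low PA as determined by the Rapid Assessment of Physical Activity Survey" and at least one of three fall-risk factors.

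Those who pass repeat their baseline. For those who do not, the whole instruction is: "If participants become ineligible---, reason(s) for ineligibility will be documented". The paragraph on comparing baselines is limited to "repeated baseline measures for subjects who choose option (a) and remain eligible for the study".

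Three other places bear on this:

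- Section 13.2 applies intention to treat to people who stop the intervention and go on giving data.
- Section 17.1 says "We will include all cases in analyses, regardless of intervention attendance rates or attrition".
- Section 18.2, among its adverse-event examples, says that a participant who becomes immobile would be withdrawn from the study because immobility is an exclusion criterion.

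**The concern.** Entry criteria protect a randomized comparison only when they are applied before allocation. Here they are applied afterwards, in some cases after weeks of the assigned course. Two of them, activity level and fall risk, sit close to the primary outcome (total activity, section 3.1) and a secondary outcome (fall rate, section 3.2). If failing the repeat screen ends a person's participation, the people left in each condition are partly chosen by something the condition may have changed. Outcomes that were never collected cannot be recovered by an analysis rule.

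**Working it through.** The plan gives no figure for delayed or re-screened participants, so there is none to reproduce. The check sets the passages side by side and then asks how large an effect could be.

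**1. What happens to someone who fails?** Section 5.2 names one action, recording the reason. It assigns the person neither to option (b) nor to continued assessments or fall calendars. Its next paragraph speaks of eligibility for the study, not for the sessions. The immobility example in section 18.2 treats meeting an exclusion during the trial as a reason to leave it. Together these support reading failure as removal, but no sentence says so.

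**2. Who could fail?**

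- *People who had started.* The RAPA criterion is met by low aerobic activity and/or low strength and balance activity. To fail it, a person must be above the limit in both. The course pushes in both directions: section 4.1 encourages Otago practice every other day and about 150 minutes of walking a week. Fall risk is lost only if none of the three factors remains.
- *People who never started.* Response to the sessions cannot explain their failure, but time or health can. The fall factor looks back one year. Thirteen waves in 48 months (section 5.1) are 48/13 = 3.7 months apart on average, so a qualifying fall can drop out of the window during a delay.
- *People in decline.* Recent leg surgery, inability to walk or a low cognitive score (section 9.2) also lead to failure.

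**3. Does other text rescue them?** Section 17.1 promises that all cases are analysed, but supplies no outcome data for someone no longer followed. Section 13.2 depends on data collection continuing, which section 5.2 does not provide for. Of the two sensitivity analyses in section 17.1, complete cases leave such people out, and worst case carried forward would give a poor outcome to someone removed for being too active.

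**4. How large could it be?** Inputs from section 17.2: 308 randomized, 15% attrition, design effect 0.20 SD.

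- Per factor level: 308/2 = 154 randomized and 154 × 0.85 = 131 completers.
- Removing a net excess of k people from one level, each d SD above its mean, shifts that mean by −k·d/(131 − k). With d = 1 (assumed), k = 2 gives 2/129 = 0.016 SD (8% of 0.20), and k = 5 gives 5/126 = 0.040 SD (20%).
- Is such an excess plausible? Assume the component has moved activity at re-screening by 0.20 SD on one normal scale with a single cutoff. The chance of exceeding the cutoff then differs between levels by at most Φ(0.1) − Φ(−0.1) = 0.080. An expected excess of 5 needs 5/0.080, about 63 delayers per level (63/154 = 41%); an excess of 2 needs about 25 (16%). Neither is rare.
- With 5 delayers per level (assumed), the expected excess is at most 5 × 0.080 = 0.4 person. The shift is 0.4/130.6 = 0.003 SD, or 1.5% of 0.20.

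This is an order-of-magnitude guide. It does not model the two-part RAPA rule, the fall-risk items, removal through decline or chance imbalance.

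**5. Power.** Use Φ(0.20·√(N/4)/√(1 − ρ²) − 1.96), with ρ = 0.8175 assumed because it puts N = 308 × 0.85 = 261.8 at 80.2% power. The plan states no ρ. Losing a further 1%, 3% or 5% of 308 (about 3, 9 or 15 people) gives 79.8%, 78.8% or 77.8%. The issue is selection, not precision.

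**The case against.** The best defence is that nothing in section 5.2 says these people are dropped. The phrase about remaining eligible may only describe who has a second baseline to compare. Section 17.1 defines the analysis set, and it is everyone. Section 13.1 expects every withdrawal to be voluntary, which fits poorly with planned removal. The immobility example concerns inability to walk, not being too active or no longer at risk of falling. And section 13.2 could cover someone who stopped for family reasons, provided data collection goes on.

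Much of this stands. Removal is an inference, and the write-up must say so. But the defence depends on data collection continuing, and that is what section 5.2 leaves out.

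A reader might go further and infer that the plan discards responders and so biases the trial toward no effect. The documents do not support that. Response can be the cause only for people who had started and who then exceed both parts of the RAPA criterion or have no fall-risk factor left. The triggers the plan names, a death in the family or sudden medical treatment, make lower activity at least as plausible. Removing people in decline would push that level's mean the other way.

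**Conclusion.** The point holds as a gap with a cheap remedy. The plan applies outcome-related entry criteria to people already randomized and does not say that those who fail stay in follow-up. This leaves room for exclusion after randomization, and sections 5.2, 13.2, 17.1 and 18.2 do not agree on it.

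The size of any bias is unknown, because the plan gives no rate. If the cases are as rare as it says, it is probably small: about 0.003 SD with 5 delayers per factor level under the assumptions above. The shifts of 8% and 20% of the design effect show only what freely chosen excesses of 2 and 5 would do; they are not estimates and should not be quoted as such. The direction is not established.

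**What to change.** Add to section 5.2, in the branch for participants who become ineligible:

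- Failing the repeat screen does not end outcome follow-up. Subject to continued consent, all post-intervention assessments and the monthly fall calendars go on.
- The participant is analysed in the randomized condition.
- The number who delay, the number who fail the repeat screen and the reasons are reported by condition.

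Write this out rather than pointing to option (b), which is the participant's choice, allows as few as one assessment and does not mention fall calendars. The text also needs to say from which date assessments are timed when the course is never completed, and that the first baseline serves as the covariate when none is repeated.

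Then reconcile section 13.2 (so that its intention-to-treat statement names this group), section 17.1 and the withdrawal example in section 18.2. Whether such a participant attends later sessions is a clinical decision for the investigators; the statistical change does not depend on it, and nothing is proposed here.

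The cost is a minor protocol and IRB modification and the follow-up of a few more participants.
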